3.2.3 Choice of outcome variables

HbA1c is the variable of choice for assessment of glycaemic control and was therefore chosen as the primary outcome variable. Because of its novel, complementary mechanism of action, dapagliflozin may have additive or synergistic HbA1c-lowering effects when given in combination with other anti-hyperglycaemic agents. Additionally, as beneficial effects on FPG, SBP and weight have been observed in other dapagliflozin studies, these variables have been chosen as key secondary objectives (see Table 4).

Table 4 Efficacy variables with related objectives and rationale

Efficacy variable	Related objective	Rationale
HbA1c	
Change from baseline in HbA1c to week 24
 
Proportion of patients achieving a therapeutic glycaemic response, defined as HbA1c <7.0%, at week 24.
 
Change from baseline in HbA1c to week 24 in patients with baseline HbA1c \geq8.0%.
 
Change from baseline in HbA1c to week 24 in patients with baseline HbA1c \geq9.0%
	
HbA1c is the clinical and regulatory parameter used to estimate glycaemic efficacy in patients with type 2 diabetes (CPMP 2002). HbA1c targets for patients with type 2 diabetes range from <6.5% (IDF 2005, AACE 2011) to <7% (ADA 2011). The degree of change in HbA1c in patients with type 2 diabetes is related to the baseline HbA1c level; patients with higher HbA1c at baseline tend to have greater reductions in HbA1c when treated with any anti-hyperglycaemic agent (Bloomgarden 2006).

Fasting Plasma Glucose	
Change from baseline in FPG to week 8 and 24.
 
Proportion of patients discontinued for lack of efficacy or rescued for failing to maintain FPG on pre-specified rescue criteria at weeks 4, 8, 16, and 24.
	
Fasting plasma glucose is well-established measures of glycaemic efficacy, and are considered by the CHMP to be acceptable secondary endpoints (CPMP 2002).

Total Body Weight	
Change from baseline in total body weight to week 24.
	
More than 85% of patients with type 2 diabetes are overweight (BMI \geq27 kg/m²) or obese (BMI \geq30 kg/m²) (CDC 2004). Weight loss is a fundamental goal for the majority of patients with type 2 diabetes since it has been shown to improve comorbid conditions such as hypertension, dyslipidemia, heart disease, osteoarthritis, and sleep apnea (NHLBI 1998).

Efficacy variable	Related objective	Rationale
Blood pressure	
Change from baseline in seated SBP to week 8.
 
Change from baseline in seated SBP to week 24.
 
Proportion of patients who achieve a seated blood pressure of <130/80 mmHg at week 24 in patients with baseline blood pressure (SBP ≥130 mmHg and/or baseline diastolic blood pressure (DBP) ≥80 mmHg).
	
The American Diabetes Association and the Joint National Committee on Prevention, Detection, Evaluation and Treatment of High Blood Pressure (JNC 2004) guidelines recommend a blood pressure target of <130/80 in patients with diabetes (ADA 2011, JNC 2004). Lowering blood pressure in patients with diabetes has been shown to reduce the risk of coronary heart disease events, stroke, retinopathy and nephropathy (JNC 2004).

Fasting lipids	
Percent change from baseline in fasting lipids (total cholesterol, low-density lipoprotein cholesterol, high-density lipoprotein cholesterol and triglycerides) to week 24.
	
Patients with type 2 diabetes have an increased prevalence of lipid abnormalities, which contributes to their high risk of cardiovascular disease (ADA 2011). For this reason, it is important to evaluate the lipid effects of anti-hyperglycaemic agents.

HOMA-2, HOMA-IR	
Change from baseline in the following parameters to week 24:
 
 - β-cell function (as measured by Homeostasis Model Assessment 2 [HOMA-2]) - Insulin resistance (as measured by HOMA-IR) - Insulin, c-peptide, proinsulin 	
β-cell dysfunction and insulin resistance contribute to the pathogenesis of type 2 diabetes; improvements in these parameters may be observed with improved glycaemic control (Poitout et al 2008).

Waist circumference	
Change from baseline in waist circumference to week 24.
	
The presence of excess fat in the abdomen out of proportion to total body fat is an independent predictor of risk factors and morbidity. Waist circumference is positively correlated with abdominal fat content (NHLBI 1998).

3.2.4 Choice of study population

Age

The upper age limit will be based on local metformin prescribing guidelines.

HbA1c

The HbA1c inclusion criterion at randomisation was selected to include patients with a wide range of glycaemic control. The lower bound of this interval (ie, 7%) reflects the most recent American Diabetes Association treatment guidelines (ADA 2011). Although other guidelines recommend treatment to lower HbA1c targets, the results of some studies suggest that these stricter targets may not be appropriate for all patients (ACCORD 2008, ADA 2011). The upper limit of this interval (ie, 10.5%) was chosen because insulin is generally the treatment of choice for patients with HbA1c values above this level (ADA 2011).

Pregnancy or breastfeeding

Dapagliflozin has not been tested in pregnant women and the risks to embryo, foetus, and infant are unknown. For this reason, women who are pregnant or breastfeeding are excluded and women of childbearing age are instructed to take precautions to avoid becoming pregnant during the study. Based on pre-clinical studies dapagliflozin must not be used in the second and third trimesters of pregnancy. For more information relating to dapagliflozin exposure and pregnancy, please refer to the IB.

Other

The purpose of the majority of the inclusion and exclusion criteria is to limit confounding factors that may complicate the interpretation of the study results (eg, corticosteroid-induced type 2 diabetes, haemoglobinopathies that would interfere with the HbA1c analyses) or to exclude patients whose safety could be compromised by participation in the study.

4. PATIENT SELECTION CRITERIA

Investigator(s) should keep a record, the patient screening log, of patients who entered pre-study screening.

Each patient should meet all of the inclusion criteria and none of the exclusion criteria for this study. Under no circumstances can there be exceptions to this rule.

4.1 Inclusion criteria

For inclusion in the study patients should fulfil the following criteria.

The following criteria apply to the enrolment, placebo lead-in and randomisation visits (Visits 1, 2, 3, and 4).

1. Provision of informed consent prior to any study specific procedures.
2. Diagnosis of type 2 diabetes mellitus.
3. Men or women age ≥ 18 years old, the upper age limit should be based on local metformin label restrictions.
4. Stable dose combination therapy of metformin ≥ 1500 mg/day and maximum tolerated dose which must be at least half maximum dose of sulfonylurea for at least 8 weeks prior to enrolment.
5. HbA1c inclusion criteria:
 - At enrolment (Visit 1) – laboratory values from screening visit:
 $\geq 7.7\%$ and $\leq 11.0\%$.
 - At the randomisation visit (Visit 4) – laboratory values from visit 3:
 $\geq 7.0\%$ and $\leq 10.5\%$.
6. For women only: Women not of childbearing potential, or women of childbearing potential who comply with the following:
 - Use a highly effective method of birth control (see below) to avoid pregnancy throughout the study and for up to 4 weeks after the study.
 - Have a negative urine pregnancy test (minimum sensitivity 25 IU/L or equivalent units of HCG) within 72 hours prior to the start of study medication and at each visit.

Definitions:

Women of Child Bearing Potential - Women between menarche and menopause who have not been permanently or surgically sterilized and are capable of procreation.

Women NOT of Childbearing Potential - Women who are permanently or surgically sterilized or postmenopausal. Permanent sterilisation includes hysterectomy and/or bilateral oophorectomy and/or bilateral salpingectomy but excludes bilateral tubal occlusion. Tubal occlusion is considered a highly effective method of birth control but does not absolutely

exclude possibility of pregnancy. (The term occlusion refers to both occluding and ligating techniques that do not physically remove the oviducts).

Post Menopausal Women - Women will be considered postmenopausal if they are amenorrheic for 12 months without an alternative medical cause. The following age-specific requirements apply:

- Women under 50 years old would be considered postmenopausal if they have been amenorrheic for 12 months or more following cessation of exogenous hormonal treatments and have FSH levels ≥ 40 mIU/mL.
- Women over 50 years of age would be considered postmenopausal if they have been amenorrheic for 12 months or more following cessation of all exogenous hormonal treatments.

Highly effective method of birth control is defined as one that results in a low failure rate (eg, less than 1 percent per year) when used consistently and correctly. The following are considered acceptable methods of contraception: Total sexual abstinence; Vasectomised sexual partner; Tubal occlusion (ligation); IUD Intrauterine Device; IUS levonorgestrel Intra Uterine System (eg, Mirina); Etonogestrel implants (eg, Implanon, Norplan); Normal and low dose combined oral contraceptive pills; Norelgestromin/EE ethinyl estradiol transdermal system; Intravaginal device (eg, EE and etonogestrel); Cerazette (desogestrel).

For inclusion in the optional genetic research, patients must fulfil the following criterion:

1. Provision of informed consent for genetic research.

If a patient declines to participate in the optional genetic research, there will be no penalty or loss of benefit to the patient. The patients will not be excluded from other aspects of the study described in this Clinical Study Protocol.

4.2 Exclusion criteria

Patients should not enter the study if any of the following exclusion criteria are fulfilled.

The following criteria apply to the enrolment, placebo lead-in and randomisation visits (Visits 1, 2, 3, and 4).

Endocrine and metabolic disorders

1. Diagnosis of Type 1 diabetes mellitus, known diagnosis of MODY or secondary diabetes mellitus.
2. History of diabetic ketoacidosis.
3. Symptoms of poorly controlled diabetes including, but not limited to, marked polyuria, polydipsia, and/or greater than 10% weight loss during the 3 months prior to enrolment.

4. FPG >270 mg/dL (>15 mmol/L) – assessed based on laboratory results from Visits 1, 2 and 3.
5. BMI >45 kg/m²
6. History of bariatric surgery (ie, any surgery to treat obesity; for example, gastric banding or procedures that involve bypassing or transposing sections of the small intestine). History of liposuction is allowed.
7. Diabetes insipidus.
8. Thyroid-stimulating hormone (TSH) and free T4 values outside normal range; an abnormal TSH value needs to be followed up with a free T4 test. Patients with abnormal free T4 values will be excluded.

Cardiovascular disorders

9. Recent Cardiovascular Events in a patient:
 - Acute Coronary Syndrome (ACS) within 2 months prior to enrolment.
 - Hospitalization for unstable angina or acute myocardial infarction within 2 months prior to enrolment.
 - Acute Stroke or TIA within 2 months prior to enrolment.
 - Less than 2 months post coronary artery revascularization prior to enrolment.
10. Congestive heart failure defined as New York Heart Association (NYHA) class IV, unstable or acute congestive heart failure. Note: eligible patients with congestive heart failure, especially those who are on diuretic therapy, should have careful monitoring of their volume status throughout the study.
11. Blood pressure:
 - At enrolment (Visit 1):
Systolic BP \geq 170 mmHg and/or diastolic BP \geq 110 mmHg.
 - At randomisation (Visit 4):
Systolic BP \geq 160 mmHg and/or diastolic BP \geq 100 mmHg.

Kidney or urological disorders

12. Measured serum creatinine value of \geq 1.5 mg/dL (133 μ mol/L) for male patients and \geq 1.4 mg/dL (124 μ mol/L) for female patients or renal function that would preclude treatment with metformin according to local guidance.
13. History of unstable or rapidly progressing renal disease.

14. Familial renal glucosuria. This condition is diagnosed as glucosuria (>1.0 mmol/L urine) in the presence of normoglycaemia in patients without the diagnosis of diabetes mellitus.
15. History of unexplained microscopic or gross hematuria, or microscopic hematuria at Visit 1, confirmed by a follow-up sample at next scheduled visit, where according to the investigator a satisfactory evaluation of hematuria has not been conducted based on guidance in Section 6.4.9.3.

Hepatic disorders

16. Severe hepatic insufficiency and/or significant abnormal liver function defined as aspartate aminotransferase (AST) >3x upper limit of normal (ULN) and/or alanine aminotransferase (ALT) >3x ULN.
17. Total bilirubin >2.0 mg/dL (34.2 µmol/L).
18. Positive serologic evidence of current infectious liver disease including Hepatitis B viral antibody IGM, Hepatitis B surface antigen and Hepatitis C virus antibody.
19. History of drug-induced liver enzyme elevations.
20. History of severe hepatobiliary disease or hepatotoxicity with any medication.

Hematologic/oncologic disorders/conditions

21. Haemoglobin <10 g/dL (<100 g/L) or 6.2 mmol/L for men; haemoglobin <9.0 g/dL (<90 g/L) or 5.9 mmol/L for women.
22. History of chronic haemolytic anaemia or haemoglobinopathies (for example, sickle cell anaemia, thalassemia, sideroblastic anaemia). Mild haemolysis due to artificial heart valves or due to sickle cell trait is not an exclusion criterion except when haemoglobin levels are too low (as defined in haemoglobin criteria above).
23. Iron deficiency anaemia with iron therapy started in the past 12 weeks prior to enrolment visit, or a recent diagnosis of iron deficiency anaemia that requires therapeutic management within the next 24 weeks in the judgement of the investigator.
24. Donation or transfusion of blood, plasma, or platelets within the past 12 weeks prior to enrolment.
25. History of malignancy within the last 5 years prior to enrolment, excluding successful treatment of basal or squamous cell skin cancer.

Infectious disease/immunologic disorders

26. Known immunocompromised status, including patients who underwent organ transplantation.

Musculoskeletal disorders

27. Creatine Kinase (CK) >3x ULN.
28. History of drug-induced myopathy or drug-induced CK elevation.

Reproductive status

29. Pregnant or breastfeeding patients.

Prohibited medications

30. Use of any anti-hyperglycaemic medications other than metformin or sulfonylurea during the 10 weeks prior to enrolment.
31. Use of weight loss medication, including but not limited to sibutramine, phentermine, orlistat, rimonabant, benzphetamine, diethylpropion, methamphetamine, and/or phendimetrazine, within 30 days prior to enrolment.
32. Treatment with systemic glucocorticoids equivalent to oral prednisolone ≥ 10 mg (betamethasone ≥ 1.2 mg, dexamethasone ≥ 1.5 mg, hydrocortisone ≥ 40 mg) per day within 30 days prior to enrolment; Treatment with single injections of systemic glucocorticoids, topical or inhaled corticosteroids are allowed.

Other standard criteria

33. Intolerance, contraindication or potential allergy or hypersensitivity to dapagliflozin, metformin, sulfonylurea, sulphonamides, DPP-4 inhibitors, placebo, or formulation excipients.
34. Any clinically significant abnormality identified on physical examination, ECG or laboratory tests, which in the judgement of the investigator would compromise the patient's safety or successful participation in the clinical study.
35. Volume depleted patients. Patients at risk for volume depletion due to co-existing conditions or concomitant medications, such as loop diuretics should have careful monitoring of their volume status.
36. Acute or chronic metabolic acidosis.
37. History of alcohol abuse or illegal drug use within the past 12 months prior to enrolment.
38. Involvement in the planning and conduct of the study (applies to both AstraZeneca and Bristol-Myers Squibb staff or staff at the study centre).

39. Previous enrolment or randomisation to treatment in the present study.
40. Previous participation in a clinical study with dapagliflozin (BMS-512148) and/or with any other SGLT2 inhibitor in which the patient received at least one dose of study medication.
41. Participation in another clinical study with an investigational product during the last 4 weeks prior to enrolment.

For the participation in the optional genetic research, patients must not have had:

42. Previous bone marrow transplant.
43. Whole blood transfusion within 120 days of the date of genetic sample collection.

Procedures for withdrawal of incorrectly enrolled patients see Section 5.3.

Note: Patient's eligibility will be assessed based on values provided by central laboratory.

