Patients will continue to monitor their FPG levels at least every second day and will continue to enter the results into the patient diary. Investigators may instruct patients to monitor their FPG more often, according to their local treatment guidelines or clinical judgement. Hypoglycaemic events should also be entered into the patient diary. For FPG monitoring procedures and assessment of hypoglycaemic events please refer to Section 6.4.9.1.

Diet and lifestyle advice will be reinforced at each visit during the double-blind treatment period, according to clinical practice.

The need for initiation of rescue therapy during 24-week double-blind treatment period will be assessed based on criteria in Table 1. Procedures for rescue are described in Section 3.1.7.

Table 1 **Criteria for initiation of rescue therapy during the 24-week double-blind treatment period**

Period	Central Laboratory FPG
From week 4 (Visit 5) to week 16 (Visit 7) including day of Visit 5 and Visit 7	FPG >240 mg/dL (13.2 mmol/l)
From week 16 (Visit 7) to week 24 (Visit 8) excluding day of Visit 7 including day of Visit 8	FPG >200 mg/dL (11.1 mmol/l)

Adjustment of background anti-hyperglycaemic medication

Metformin cannot be down titrated during the treatment period.

Sulfonylurea can be down titrated only once during the treatment period to mitigate recurrent hypoglycaemic events at the discretion of the investigator.

No up-titration of metformin and sulfonylurea during the treatment period is allowed.

Adjustment of anti-hypertensive medication

Background anti-hypertensive medications should not be increased or decreased between weeks 0-8 (Visits 4, 5 and 6). Exceptions to this rule are:

- Patients with confirmed SBP ≥ 160 mmHg or DBP ≥ 100 mmHg on or after week 4 should return for a follow-up visit within 1 week. If the BP is still elevated, changes in background blood pressure medication should be made.
- Blood pressure medication may be decreased if in the investigator's judgement the patient has symptomatic hypotension or has documented orthostatic hypotension during a study visit.

After week 8, changes in anti-hypertensive medication may be made as needed for appropriate blood pressure management. All medication changes, including dose modifications, should be recorded in the Medication module of the eCRF.

3.1.5 28-week site- and patient-blinded Extension period (Visits 8-11, week 24 to week 52)

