6.4.9.1 Fasting plasma glucose concentrations and hypoglycaemic events

Patient self-monitoring of FPG is performed in order to reduce the risks associated with prolonged hyperglycaemia and to confirm symptoms of hypoglycaemia. Patients will be asked to perform self-monitoring of FPG using glucometers provided by AstraZeneca. The patients will receive instructions for the use of the glucometer according to the manufacturer's instructions.

FPG should be self-monitored at least every second day between visits 2 and 8 and at least once a week between visits 8 and 11. The results should be recorded in the patient diary, which will be collected and reviewed by the study personnel at each visit starting with Visit 3; a print-out will be stored in the investigator study file. A new diary will be dispensed to the patient at each of these visits.

The memory of the glucometer should be reviewed and compared with the readings in the patient's diary. The glucose values should be reviewed by the study personnel to identify any unusually high or low values, and to confirm that self-monitoring was performed by the patient. If fingerstick glucose values are discordant with central laboratory results or with clinical symptoms, the patient's glucometer should be tested and the glucometer instructions should be re-reviewed with the patient.

If self-monitored FPG is
above 240 mg/dL (13.2 mmol/L) from week 4 (Visit 5) to week 16 (Visit 7),
or above 200 mg/dL (11.1 mmol/L) from week 16 (Visit 7) to week 52 (Visit 11),
the patient should repeat the FPG on the same day.

If the second FPG value is above 240 mg/dL (13.2 mmol/L) or 200 mg/dL (11.1 mmol/L), respectively, the patient should contact the study centre and be scheduled for a central laboratory FPG (or HbA1c after Visit 8) measurement within one week.

If central laboratory values are similar, the patient should receive rescue therapy.

A separate section in the eCRF will be used to document all reported episodes of hypoglycaemia. The patients will be asked to always check their blood glucose if they develop symptoms suggestive of hypoglycaemia and to record specific symptoms in the patient diary. The Investigator is responsible for questioning the patient about all symptoms reported in the diary and for determining if they meet the clinical definition of hypoglycaemia. Only symptoms and/or blood glucose values that meet the definition of hypoglycaemia should be reported on the hypoglycaemia eCRF pages.

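### Two decision thresholds carry wrong mmol/L equivalents: the female haemoglobin limit of 9.0 g/dL (printed 5.9, should be 5.6) and the rescue FPG limit of 240 mg/dL (printed 13.2, should be 13.3)

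*Protocol*

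**What the plan says.** **Haemoglobin.** Criterion 21 in section 4.2 excludes men at "Haemoglobin <10 g/dL (<100 g/L) or 6.2 mmol/L for men" and women at "haemoglobin <9.0 g/dL (<90 g/L) or 5.9 mmol/L for women". The mmol/L figure is joined by the word or, so it reads as a limit in its own right. Section 4 says of the criteria: "Under no circumstances can there be exceptions to this rule". Criterion 22 refers back to the same haemoglobin limits. The note closing section 4.2 says eligibility rests on central-laboratory values.

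**Fasting plasma glucose.** Table 1 (section 3.1.4) starts rescue from week 4 to week 16 at "FPG >240 mg/dL (13.2 mmol/l" and from week 16 to week 24 at "FPG >200 mg/dL (11.1 mmol/l". Section 6.4.9.1 repeats the first pair for self-monitored readings, "above 240 mg/dL (13.2 mmol/L) from week 4 (Visit 5) to week 16 (Visit 7", and again for the repeat test: "If the second FPG value is above 240 mg/dL (13.2 mmol/L) or 200 mg/dL (11.1 mmol/L), respectively". Elsewhere glucose is paired as "FPG >270 mg/dL (>15 mmol/L" (criterion 4) and, in the hypoglycaemia definitions of section 6.4.9.1, as 63 mg/dL with 3.5 mmol/L and 54 mg/dL with 3.0 mmol/L.

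**The concern.** Each threshold is stated in more than one unit, and the units disagree, so one laboratory result can give two answers to the same rule.

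For haemoglobin the rule decides entry to the trial, and no exceptions are allowed. For FPG the rule decides rescue. Under sections 11.1.2 and 12.2.1, the last value on or before the first rescue dose is carried forward, so the rescue decision fixes which HbA1c value enters the primary analysis. The proportion of patients rescued or discontinued for lack of efficacy by weeks 4, 8, 16 and 24 is also a secondary comparison (section 2.2.2).

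**Working it through.** All conversion ratios below come from the protocol's own pairs.

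**Haemoglobin**

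1. Ratio from the male pair: 6.2 / 10 = 0.620 mmol/L per g/dL. The figure 6.2 may stand for anything from 6.15 to 6.25, so the ratio lies between 0.615 and 0.625.
2. Ratio from the female pair as printed: 5.9 / 9.0 = 0.656, outside that range.
3. Female limit at the male ratio: 9.0 × 0.620 = 5.58 (5.54 to 5.63 over the range), so 5.6 mmol/L. The printed 5.9 is not reproduced.
4. Reading 5.9 mmol/L back: 5.9 / 0.620 = 9.52 g/dL (5.9 / 0.625 = 9.44 to 5.9 / 0.615 = 9.59).
5. Since 9.0 g/dL and 90 g/L agree, the mmol/L figure is the one that is out, by about 0.5 g/dL.

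**FPG**

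| Pair (mg/dL and mmol/L) | Ratio | Ratio allowing for rounding of mmol/L to one decimal |
|---|---|---|
| 270 and 15 | 18.00 | printed as a whole number |
| 200 and 11.1 | 18.02 | 17.94 to 18.10 |
| 63 and 3.5 | 18.00 | 17.75 to 18.26 |
| 54 and 3.0 | 18.00 | 17.70 to 18.31 |
| 240 and 13.2 (as printed) | 18.18 | 18.11 to 18.25 |
| 240 and 13.3 (corrected) | 18.05 | 17.98 to 18.11 |

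1. The decisive comparison is with 200 and 11.1, in the same table. Its upper bound is 200 / 11.05 = 18.10. The printed pair needs at least 240 / 13.25 = 18.11. The ranges do not meet, so rounding does not explain 13.2. The 63 and 54 pairs agree at 18.0 but are too coarse to settle the matter alone.
2. Converted value: 240 / 18.02 = 13.32, or 240 / 18.00 = 13.33. Both round to 13.3, and truncating gives 13.3 as well.
3. A shortened factor of 0.055 does give 240 × 0.055 = 13.2. It would also give 200 × 0.055 = 11.0, and Table 1 prints 11.1.
4. Reading 13.2 mmol/L back: 13.2 × 18.00 = 237.6 and 13.2 × 18.02 = 237.8 mg/dL. The discordant band is about 2 mg/dL wide, ending at 240.

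**How many FPG readings fall in the band.** The protocol gives no FPG distribution. Assume a normal distribution with mean 150 to 180 and SD 35 to 55 mg/dL.

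- P(237.8 < FPG < 240) is 0.10% at mean 150, SD 35, and 0.90% at mean 180, SD 55.
- Times 216 randomised patients: 0.2 to 1.9 patients per visit.
- If mmol/L is reported to one decimal (a further assumption), only a result of 13.3 is affected. It covers 13.25 to 13.35, which is 238.7 to 240.5 mg/dL. The discordant part, 238.7 to 240, holds 0.06% to 0.53% of readings, or 0.1 to 1.1 patients per visit.

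The 240 mg/dL limit applies at three scheduled visits: weeks 4, 8 and 16.

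**Other pairs checked.** The creatinine limits (1.5 mg/dL with 133 µmol/L, 1.4 with 124) and the bilirubin limit (2.0 mg/dL with 34.2 µmol/L) in section 4.2 are right.

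**The case against.** The arithmetic is not in dispute; the weight is. Five points can be made.

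- **Handling is central.** Under section 3.1.7 investigators are blinded to FPG after randomisation, and the laboratory reports the exact value once a patient meets the rescue criterion. About 50 sites are not each choosing a unit, and any cut-off applies equally to both blinded arms. This stands as the main mitigation. It does not say which printed number the laboratory programs: uniform use of 5.9 mmol/L would uniformly exclude women whom 9.0 g/dL admits.
- **The 6.4.9.1 figures are not rescue criteria.** They prompt a repeat self-test and then a central measurement. For the Table 1 limit, section 3.1.7 lets the investigator retest when the diary does not confirm the value. Both points are correct, and they shrink an already small FPG effect. Patients using mmol/L would still act on the wrong figure.
- **The intended unit can be guessed.** The comparison sign sits on g/dL, g/L and mg/dL, and the mmol/L figures carry none in these two rules. This is a fair inference, but it is not stated, and in criterion 21 the mmol/L figure is offered as an alternative limit.
- **The haemoglobin error is conservative.** It acts before randomisation, so it cannot bias the treatment comparison. It can only exclude extra women, never admit one whom the g/dL limit would exclude. This stands. The number of women affected cannot be estimated from the protocol.
- **The FPG count rests on assumed means and SDs**, and 1.9 per visit is its extreme corner with no allowance for retests. This also stands.

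**Conclusion.** Both mismatches are certain as printed and follow from the protocol's own figures. The haemoglobin error is about 0.5 g/dL (a band of 9.0 to about 9.5 g/dL, women only) in an eligibility rule with no exceptions. The FPG error is a slip of 0.1 mmol/L, or about 2 mg/dL, confined to weeks 4 to 16. It touches at most about two patients per visit on assumed distributions, and fewer with one-decimal reporting or retesting.

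No misclassification has been shown. The effect on the primary estimate is at most very small, and sample size, model and error control do not depend on either figure. They should be corrected because they are operating thresholds that give two answers, not because the trial's result is at risk.

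**What to change.** Print 5.6 mmol/L for women in criterion 21, and 13.3 mmol/L in Table 1 and at both places in section 6.4.9.1. Alternatively, state that the g/dL and mg/dL values govern; this also removes the residual ambiguity from one-decimal rounding. Then check the central-laboratory eligibility and rescue flags, and the patients' glucometer instructions, against the corrected values.

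The cost is an administrative correction of four printed values plus that check.
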